### **6.6.2 Urinalysis**

Urinalysis will include assessment of protein, blood, leukocytes, glucose, ketones, bilirubin, urobilinogen, pH, and specific gravity and microscopic analysis. In phase 1, this testing will occur at baseline, 2, 4 and 6 weeks, and in phase 2 at baseline, 2, 4 and 6 months.

Lab results do not need to be resulted and reported prior to dosing.

## **6.7 Research Laboratory Testing**

Plasma and serum will be collected for biomarker analysis. Sample collection, processing and storage will be standardized. Coded samples will be sent to NICHD Biorepository for long-term storage. Testing may be performed in clinical or research laboratories. Research testing will include, but is not limited to the following:

Markers of cholesterol homeostasis (phase 1: Baseline, 2, 4 and 6 weeks; 0.5 ml/time point; 2 mls total over 6 weeks; phase 2: Baseline, 2, 4 and 6 months; 0.5 ml/time point; 2 mls total over 6 months)

1. Trihydroxycholanic acid glycine conjugate (bile acid biomarker)
2. Cholestan-3 $\beta$ ,5 $\alpha$ ,6 $\beta$ -triol
3. PPCS/Lipid-509

Plasma lipidomics (phase 1: Baseline and 6 weeks; 0.5 ml/time point; 1 ml total over 6 weeks; phase 2: 6 months; 0.5 ml/time point; 0.5 ml total over 6 months)

1. Sphingolipids: sphingoid bases, ceramides, glucosylceramides, lactosylceramides, gangliosides
2. Lysosphingolipids: lyso-sphingomyelin

Additional biomarkers for NPC (phase 1: Baseline, 2, 4, and 6 weeks; 1.75ml/time point; 7mls over 6 weeks; phase 2: Baseline, 2, 4, and 6 months; 1.75 ml/time point; 7 mls total over 6 months)

- Serum 24(S)-hydroxycholesterol
- Serum 27-hydroxycholesterol
- Serum neurofilament light chain

Lab results do not need to be resulted and reported prior to dosing.

## **6.8 Future Research and Other Testing**

Other blood, cellular or urine biomarkers may be assessed. At the discretion of the investigator, blood, and urine may be collected and saved for future research.

Biomarkers of inflammation (phase 1: Baseline, 4 and 6 weeks; 0.5 ml/time point; 1.5 mls total over 6 weeks; phase 2: 6 months; 0.5 ml/time point; 0.5 mls total over 6 months)

Such as galectin 3 (LGAL3), cathepsin D, lysozyme, C-Reactive Protein High Sensitivity (hsCRP), and inflammatory cytokines

Bile acids (phase 1: Baseline, 2, 4 and 6 weeks; dried blood spot; total volume minimal; phase 2: Baseline, 2, 4 and 6 months; dried blood spot; total volume minimal)

The blood, urine, and derivatives thereof (e.g., peripheral B-cells, ribonucleic acid (RNA) or deoxyribonucleic acid (DNA)), collected under this protocol, can be stored for future research not specifically lined in this protocol. Such research could involve, but is not limited to, proteomic, genomic, biochemical, metabolomic, and molecular analysis of these samples. Corresponding clinical data may also be used for future research. Future research using these samples will relate to Niemann-Pick disease or other projects specifically approved by an Institutional Review Board. Priority will go to studies related to Niemann-Pick disease. This research may occur at the NIH or at outside laboratories. If sent to outside laboratories samples will be coded and patient identifiers will be removed. If a biospecimen is sent to a clinical laboratory for testing, identifiers will not be removed and the result will become part of the medical record.

## **7. Human Subjects Protections**

### **7.1 Institutional Review Board**

This protocol and informed consents will be reviewed and approved by the Washington University Institutional Review Board (IRB). The IRB will meet all FDA requirements governing IRBs (Code of Federal Regulations (CFR), Title 21, Part 56).

### **7.2 Ethical Conduct of the Study**

The investigator will conduct this study in compliance with FDA regulations.

### **7.3 Patient Information and Informed Consent**

Written informed consent will be obtained from parents or guardians prior to any intervention under this protocol. The informed consent form (ICF), as specified by the Washington University IRB, must follow the Protection of Human Subjects regulations listed in the CFR, Title 21, Part 50.

Verbal or written screening for inclusion/exclusion criteria may be conducted prior to obtaining informed consent.

The background of the proposed study and the benefits and risks of the procedures and study will be explained to the guardians. The Principal Investigator or an Associate Investigator will obtain consent. The original signed and dated informed consent will be placed into subject's medical record. A copy will be given to the guardian.

### **7.4 Subject Selection**

Subjects will be diagnosed as having NPC based on criteria specified in Section 5.4.1. For potential subjects for whom a definitive diagnosis is not available, the researchers may provide NPC-specific diagnostic testing before subject enrollment.

Information regarding this study will be distributed through parent support organizations such as, but not limited, to National Niemann-Pick Disease Foundation (NNPDF), Ara Parseghian Medical Research Foundation (APMRF), Dana's Angels Research Trust (DART), Support of Accelerated Research for Niemann-Pick Type C (SOAR-NPC), and Fight NPC.

Information about the study will be posted on ClinicalTrials.gov.

### **7.5 Gender and Ethnic/Racial Background**

Subjects of either gender or any ethnic/racial background will be eligible for this study. NPC1 is an autosomal recessive disorder, thus gender distribution is expected to be equal. NPC1 is a panethnic disorder, but several genetic isolates, due to founder effects, exist. These include Acadians in Nova Scotia, Hispanics in parts of Colorado and New Mexico, and a Bedouin Group in Israel. It is expected that the subject's ethnic/racial demographics will reflect disease demographics. The small size of this study could result in random skewing of the expected distribution for either gender or ethnic/racial background.

This is a pilot study involving a small sample size from a limited patient population with a rare disease. Subjects will be screened to determine if they are eligible to participate in the trial prior to enrollment. Selection bias will be minimized as much as possible by screening all interested NPC subjects until the maximum accrual number has been met.

### **7.6 Research Involving Children**

This study will involve physically and cognitively impaired children. Consent will be obtained from parents/guardians. If possible, consent will be obtained from both parents/guardians. Verbal consent can be given by a second parent/guardian if only one parent has accompanied the child to the study site. Due to the age range included in this study assent will not be possible.

This study is consistent with 45 CFR 46.405. Specifically, the research involves greater than minimal risk but presents the prospect of direct benefit to the individual child involved in the research. Given that NPC is a progressive, lethal neurological disorder with no FDA approved therapy, the risks in this protocol are commensurate with the disease process. The preclinical data in animal models suggest that the risk is justified by the potential benefit should this drug prove to be efficacious in humans.

## **7.7 Subject Withdrawal**

Guardians/parents will be informed that they have the right to withdraw from the study at any time for any reason without prejudice to their medical care. Subjects may be withdrawn from the study for any of the following reasons:

- Parent/guardian request
- Parent/guardian is unwilling or unable to comply with the protocol
- Medical reason, at the discretion of the Investigator or Medical Monitor
- Occurrence of the following:
  - a. any Grade 3 AE (per NCI's CTCAE) possibly or definitely related to study drug
  - b. any Grade 4 toxicity
  - c. any subject with pulmonary complications or evidence of renal injury
  - d. determination that the limit of safety and/or tolerability has been reached. In the context of adrabetadex administration, limit of tolerability is defined as a new oxygen requirement or evidence of renal injury.
  - e. evidence of development or worsening of liver synthetic function (monitored by serum albumin and PT) or evidence of development or worsening of hepatic encephalopathy (monitored by serum ammonia levels).

Although study treatment will cease, subjects will be encouraged to remain on study in order to collect all of the data prescribed in the protocol. The reasons for subject withdrawal will be recorded in the subject's CRF.

For a withdrawal due to a safety issue, subjects will be followed until the safety issue is resolved or returns to baseline level. Additionally, any appropriate referrals will be made as needed.

Any usable data from withdrawn subjects will be included in safety and efficacy evaluations. Withdrawn subjects may be replaced.

## **7.8 Adverse event assessments**

Adverse events will be assessed using CTCAE version 5.0. Safety and tolerability of adrabetadex will be determined as presented in Table 1 except for respiratory and audiological complications.

Subjects will be withdrawn or dose decreased if they experience systemic (decreased blood pressure, heart rate, allergic rash, wheezing), respiratory (sustained increased respiratory rate over 30 minutes or decreased SaO2 (<90%)), or central nervous system (altered level of consciousness, seizures) symptoms during drug infusion or within 2 hours post-infusion. Subjects will be withdrawn or dose decreased if CXR demonstrates pulmonary infiltrates likely related to drug administration. If the etiology of pulmonary infiltrates is not known, they dose may be repeated and a subsequent CXR obtained. If the subsequent CXR demonstrates increased pulmonary infiltrates, subject will be withdrawn.

**Table 1. Decision Table for Evaluating the Safety and Tolerability of IV adrabetadex in Individual Subjects (respiratory and audiological excluded)**

	Safety Profile of Individual Patient	Safety Decisions*
A	No AEs and no SAEs or Any number of Common Terminology Criteria for Adverse Events (CTCAE) Grade 1 drug-related AEs; ≤ 1 CTCAE Grade 2 drug-related AE; or	Repeat the current dose
B	2 CTCAE Grade 2 drug-related AEs (or	Repeat the current dose, Study a lower dose (if applicable)
C	≥ 3 CTCAE Grade 2 drug-related AEs or ≥ 1 drug-related SAE	Study a lower dose, or withdraw the subject and Evaluate the risk/benefit profile for dose escalation of other subjects
D	Any CTCAE Grade 3 drug related AE; Any CTCAE Grade 4 drug-related AE; Any subject with drug-related pulmonary complications or thromboembolic complications Determination that the limit of safety and/or tolerability has been reached	Withdraw the subject and Evaluate the risk/benefit profile in other subjects for dose escalations to or above the dose resulting in Grade 3 toxicity and Temporarily or permanently halt study, pending DSMC review, if two subjects develop the same Grade 3 toxicity or if any subject develops a Grade 4 toxicity

### **7.9 Discontinuation or Temporary Suspension of the Study**

The DSMC or Principal Investigator may terminate this study at any time for safety or administrative reasons. The DSMC or Principal Investigator will terminate the study if the occurrence of AEs or other findings suggests an unacceptable risk to the health of the subjects. The study will be interrupted if two subjects, based on two concurrent assessments, develop the same Grade 3 drug-related adverse event (unless related to disease progression of NPC), or if any subject that develops a Grade 4 adverse event, (unless the AEs are of an accidental nature that could not be reasonably attributable to adrabetadex or related to disease progression of NPC). Following review by the DSMC, the study may be resumed as planned, resumed with subjects at a lower dose or discontinued.

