## **6.5 Audiological Evaluation.**

An audiological evaluation will be obtained at baseline and at conclusion of phase 1 of the study. Audiology assessment will be performed using otoacoustic emissions (OAE). This test does not require sedation.

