##### **11.4.3 Review of High Frequency Hearing Loss**

Although not anticipated at the doses being evaluated, high frequency hearing loss is an expected complication of adrabetadex administration.

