#### **11.6 Documentation of Adverse Events**

Subjects will be evaluated and interviewed to identify AEs during the course of the study. AEs may also be identified through clinical and neurological examinations, laboratory tests, etc. Any events occurring prior to dosing will be recorded on the Medical History CRF. Events occurring after administration of the first dose of study medication will be recorded on the AE CRF. AE that occur up to and including 30 days after administration of the last dose of study drug must be reported.

All AEs spontaneously reported by the subject or in response to a question from study personnel or revealed by observation, physical examination, or other diagnostic procedures will be recorded on the Adverse Event Form for that visit. Any clinically relevant deterioration in laboratory assessments or other clinical findings is considered

an AE and must be recorded on the AE CRF, unless otherwise stated in the protocol. AE information recorded on AE CRFs will be entered into the database on an ongoing basis.

For SAEs, a Serious Adverse Event Form must also be completed with as much information as possible and submitted in the time frame described below. When new significant information is obtained as well as when the outcome of an event is known, the Investigator should record the information on a new SAE form. If the subject was hospitalized, a copy of the discharge summary and any other relevant hospital records (e.g., admission report, laboratory test results, etc., must be included as part of the patient medical file).

All AEs considered to be related to study medication and all SAEs will be followed until resolved or until stable.

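### Section 7.9 attaches an undefined concurrency condition to the two-subject Grade 3 halt; Table 1 row D does not, and for hearing Section 7.9 is the only two-subject rule

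*Combined protocol and SAP*

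**What the plan says.** The protocol states the two-subject Grade 3 halt twice.

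- **Section 7.9:** "The study will be interrupted if two subjects, based on two concurrent assessments, develop the same Grade 3 drug-related adverse event", with the exemption "unless related to disease progression of NPC". The same sentence adds a single-subject trigger, "or if any subject that develops a Grade 4 adverse event", which carries no concurrency condition but has its own exemptions for accidental events and NPC progression.
- **Section 7.8, Table 1 row D:** the study is halted, temporarily or permanently, pending DSMC review "if two subjects develop the same Grade 3 toxicity or if any subject develops a Grade 4 toxicity". Row D has no condition on assessments and states no NPC-progression exemption.

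Section 7.8 limits the reach of Table 1: safety and tolerability "will be determined as presented in Table 1 except for respiratory and audiological complications". The table's title repeats that exclusion. Respiratory compromise has its own subject counts in Section 11.4.2. The section on hearing, 11.4.3, consists of one sentence: "Although not anticipated at the doses being evaluated, high frequency hearing loss is an expected complication of adrabetadex administration". It gives no count, grade or action.

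On hearing tests, Section 6.5 says: "An audiological evaluation will be obtained at baseline and at conclusion of phase 1 of the study". The test is OAE, without sedation. On follow-up, Section 11.6 says: "All AEs considered to be related to study medication and all SAEs will be followed until resolved or until stable".

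**The concern.** A mandatory halt should give the same answer whoever applies it. Here one version turns on a phrase that can be read in several ways: each infant's event confirmed at a second assessment, two tests at one visit, findings in two infants at about the same time, or agreement between two assessors. The other version has no such condition, and nothing says which prevails.

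For hearing there is no second version to fall back on. Section 11.4.3 calls hearing loss an expected complication of the drug, though not at these doses, and Section 8.2 reports apparently irreversible deafness in cats at higher doses. If two infants had a drug-related Grade 3 hearing event, whether the fixed count had been reached would be argued after the fact.

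**Working it through.** The protocol states no operating characteristic for this rule, so there is no figure to reproduce. The check compares the sections and then applies each reading of the phrase to the hearing schedule.

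**Step 1. The two versions side by side**

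| | Section 7.9 | Table 1 row D |
|---|---|---|
| Subjects with the same Grade 3 event | 2 | 2 |
| Condition on assessments | two, concurrent; undefined | none |
| NPC-progression exemption | stated | not stated |
| Audiological events | not excluded | excluded |
| Consequence | interruption, DSMC review | halt pending DSMC review |

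**Step 2. Which two-subject rule reaches which event**

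- *Neither respiratory nor audiological:* 7.9 and row D both apply. Two infants with the same drug-related Grade 3 event months apart meet row D, so the study halts whatever 7.9 means.
- *Respiratory:* Section 11.4.2 has its own counts, two subjects at 500 mg/kg and three in Cohort 2.
- *Audiological:* row D is excluded and 11.4.3 has no trigger. Only 7.9 remains.

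**Step 3. The readings applied to scheduled OAEs**

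Inputs: one post-dose OAE per infant, at the end of Phase 1 (Section 6.5); 12 infants, six per cohort (Section 5.6).

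- *Confirmation within an infant, or two tests at one visit:* this needs two post-dose OAEs. One is scheduled, so 0 of 12 infants can qualify from scheduled tests alone.
- *Same time in two infants, different cohorts:* Cohort 2 starts only after the DSMC has reviewed Phase 1 data from all six Cohort 1 infants (Section 5.6). End-of-Phase-1 OAEs in different cohorts therefore cannot coincide.
- *Same time in two infants, same cohort:* Section 5.3 expects about four enrolments a year and a seven-week Phase 1. With even spacing, enrolments are 52 / 4 = 13 weeks apart, and one infant's Phase 1 ends 13 − 7 = 6 weeks before the next begins. At 12 infants in four years, which is 3 a year, the spacing is 52 / 3 = 17.3 weeks. Enrolment will not be exactly even, so coincidence would be rare but is not impossible.
- *Two assessors of one result:* the schedule does not rule this out, but the protocol does not provide for it either.

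**Step 4. Unscheduled tests**

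Section 11.6 follows related adverse events until resolved or stable, and Section 7.7 follows infants withdrawn for safety. A second hearing assessment after a finding is therefore likely and could supply confirmation. No repeat OAE is specified, however, and 7.9 does not say whether one would count.

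**Step 5. What cannot be computed**

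A probability of triggering the rule would need the Grade 3 hearing risk and a way to turn an infant OAE result into a CTCAE grade. The documents give neither, so none is offered.

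**The case against.** The strongest reply is that little protection is lost, and most of that reply stands.

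- Outside hearing, row D halts the study whatever 7.9 means. A reader might infer that two widely separated Grade 3 events could pass without a halt. For events within Table 1, the documents do not support that.
- A reader might also infer that hearing has no safeguard. It has several. Section 7.9 interrupts for one Grade 4 event and requires termination if the risk is unacceptable. Sections 5.6 and 7.7 permit withdrawal for a related Grade 3 event, with no audiological exclusion. The DSMC reviews Phase 1 data from all of Cohort 1 before Cohort 2, and safety data after the first two completers and each later one (Sections 11.4 and 11.5). Completing the study may there mean completing Phase 2, but earlier and ad hoc reviews are allowed.
- An interruption under 7.9 is a pause, and the study may then resume as planned.
- The phrase may be a deliberate confirmation requirement. That is possible, but then the protocol should say so and provide the second test.
- Deleting the phrase does not by itself make a hearing rule workable or make the two versions identical. OAE results would still have no stated grade, row D would still lack the NPC-progression exemption, and Table 2 lists progressive high frequency hearing loss as associated with NPC1. This is correct, and it limits what the change achieves.

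The enrolment arithmetic bears on the same-time reading only. It does not measure how often the rule would fail.

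What the reply leaves standing is the conflict in the text. The DSMC and withdrawal provisions rest mainly on judgement and the Grade 4 trigger does not cover Grade 3, so the one fixed two-subject count that reaches hearing remains unclear.

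**Conclusion.** The point holds as a minor correction to a safety rule. Sections 7.8 and 7.9 state one mandatory halt in two forms, and the extra condition in 7.9 is undefined. For events within Table 1 the effect is on wording only. For hearing, 7.9 is the sole two-subject rule. Scheduled testing cannot meet it on a confirmation or one-visit reading (0 of 12 infants) and would rarely meet it on a same-time reading.

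The conclusion on confirmation rests on the schedule in Section 6.5 alone. The word *rarely* also rests on the expected enrolment rate and roughly even spacing. The documents do not support a claim that hearing events would go unreviewed, or any figure for how often a warranted halt would be missed.

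**What to change.** 1. In Section 7.9, delete the condition between the first two commas of the interruption sentence.
2. In 7.9 and row D, state that drug-related Grade 3 events of the same type count cumulatively across subjects, whenever they occur.
3. Use the same NPC-progression exemption in both places. Without this step the two versions would still differ.
4. In Section 11.4.3, state that the 7.9 rule covers audiological events.
5. If confirmation within a subject is intended, put it in a separate sentence and, for hearing, name the repeat OAE that would supply it.

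The cost is a short wording amendment. No new data are needed unless a repeat OAE is added, and that test needs no sedation. The downside is a somewhat higher chance of a temporary pause for DSMC review. The change does not settle how an OAE finding is graded, which would need its own sentence.

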### 11.3 Severity of an Adverse Event

Severity will be graded according to the National Cancer Institute (NCI) Common Terminology Criteria for Adverse Events (CTCAE), Version 5.0 (Published: 27 NOV 2017; v.5.0):

**Grade 1** Mild; asymptomatic or mild symptoms; clinical or diagnostic observations only; intervention not indicated.

**Grade 2** Moderate; minimal, local or noninvasive intervention indicated; limiting age-appropriate instrumental activities of daily living (ADL).

Grade 3	Severe or medically significant but not immediately life-threatening; hospitalization or prolongation of hospitalization indicated; disabling; limiting self-care ADL.
Grade 4	Life-threatening consequences; urgent intervention indicated.
Grade 5	Death related to AE.

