#### **11.4 Monitoring of Adverse Event Data**

The investigators will review each subject weekly during an admission. This may be by group email or conference call.

A local monitor and an independent Data Safety Monitoring Committee (DSMC) will review data on subjects completing and enrolled in the study. Review will occur after the first two subjects complete the study, and after each additional subject completes the study. Review may occur earlier if indicated by clinical circumstances.

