#### **11.5 Data Safety Monitoring Committee**

An independent Data Safety Monitoring Committee (DSMC) will review safety data from this study after the first two subjects complete the study and after each additional subject completes the study. Members will be “independent” in that they have no other involvement in the study. The DSMC will review data from each cohort prior to dose escalation. The DSMC will submit brief safety reports to the sponsor-investigator regarding the safety and progress of the trial. The DSMC may also meet ad hoc at the request of the sponsor-investigator. A local monitor, also independent to the study, will review reports to and from the DSMC. Reports from the DSMC and local monitor will be submitted to the institutional IRB along with a recommendation from the local monitor as to whether the study should continue with modification, continue without modification, or terminate.

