## **11.7 Notification about Serious Adverse Events and Serious Unexpected Adverse Reactions**

### **11.7.1 Investigator Reporting**

Investigators must report any SAE, whether or not considered drug related, including those listed in the protocol or Investigator Brochure. The report must include an assessment of whether there is a reasonable possibility that the drug caused the event.

The study site will document all SAEs that occur (whether or not related to study drug) on the appropriate SAE form. The collection period for all SAEs will begin after informed consent is obtained and end after procedures for the final study visit have been completed.

All SAEs must be submitted within 24 hrs and will be reviewed by the principal investigator or qualified designee and reported to the FDA and IRB according to applicable regulations and guidance. The site, within 48hrs, will submit all copies of the submitted MedWatch Form FDA 3500 to [[contact]](mailto:[contact]).

SAE's will be reported to the responsible IRB per institutions policy.

SAE Reporting Contact Information:

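### The two grade-based study-halt clauses (7.9 and Table 1 row D) stop at Grade 4 and omit death, and row D requires withdrawal for pulmonary events that Table 1 says it excludes

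*Combined protocol and SAP*

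**What the plan says.** **Study-level halt.** Section 7.9 interrupts the study for two subjects with the same drug-related Grade 3 event, or "if any subject that develops a Grade 4 adverse event". It exempts accidental events that cannot reasonably be attributed to adrabetadex, and NPC progression. On restarting it says: "Following review by the DSMC, the study may be resumed as planned, resumed with subjects at a lower dose or discontinued". In Table 1 (section 7.8), row D halts the study temporarily or permanently, pending DSMC review, "if two subjects develop the same Grade 3 toxicity or if any subject develops a Grade 4 toxicity".

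**Grading.** Section 11.3 adopts CTCAE version 5.0. Grade 4 is a life-threatening event. Grade 5 is listed separately as "Death related to AE".

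**Other routes by which a death is acted on.** Section 7.9 also provides: "The DSMC or Principal Investigator will terminate the study if the occurrence of AEs or other findings suggests an unacceptable risk". Section 11.7.1 says: "All SAEs must be submitted within 24 hrs and will be reviewed by the principal investigator or qualified designee". Section 11.5 adds: "The DSMC may also meet ad hoc at the request of the sponsor-investigator". Section 11.4 schedules DSMC and local-monitor review by subject completion ("Review will occur after the first two subjects complete the study, and after each additional subject completes the study") and allows it earlier if clinical circumstances call for it.

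**Respiratory events.** The text of 7.8 and the title of Table 1 both take respiratory complications out of the table. The text of 7.8 then gives its own rule: respiratory signs around an infusion, or chest X-ray infiltrates likely due to drug, lead to withdrawal or a lower dose. Row D nevertheless lists drug-related pulmonary complications among its criteria, and its first action is to withdraw the subject.

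**The concern.** A halt rule should be at least as strict for a fatal event as for a non-fatal one. Here a Grade 4 event from which an infant recovers interrupts the study until the DSMC has reviewed it. A drug-related death has no interruption attached to its grade. The subjects are infants enrolled at 0 to 6 months. Section 2.4 says their liver disease can progress to liver failure, and section 8.2 warns that the experimental infusion could itself cause death. A death on study is therefore foreseeable, and whether the other infants' dosing pauses should not depend on how staff read a table.

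The pulmonary conflict matters for the individual infant. For a drug-related infiltrate, the text of 7.8 leaves open continuing on a lower dose, whereas row D ends treatment.

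**Working it through.** No sample size, rate or error probability enters this point, so the check is a comparison of the rules as written.

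**Step 1. Where does a drug-related death land?**

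| Rule | What it names | Study halt? | Does it name death? |
|---|---|---|---|
| 7.9 interruption | Grade 3 (two subjects, same event); any Grade 4 | Yes | No |
| Table 1 row D, criteria | Drug-related Grade 3 or 4; drug-related pulmonary or thromboembolic complications; limit of safety or tolerability reached | Only through the halt clause | No |
| Table 1 row D, halt clause | Grade 3 (two subjects, same event); any Grade 4 | Yes | No |
| Table 1 row C | At least one drug-related SAE | No: lower dose or withdraw, plus risk/benefit evaluation for escalation in others | Indirectly, since 11.1 lists death as an SAE outcome |
| 7.9 unacceptable-risk clause | A judgement, with no grade or count | Yes (termination), once the judgement is made | Indirectly |
| 11.4 and 11.5 early or ad hoc review | Clinical circumstances, or the sponsor-investigator's request | Not by itself | Indirectly |

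Study-halt clauses triggered by grade: 2. Those naming Grade 5 or using 'or higher': 0. On a literal reading, row C is the row that directly reaches a drug-related death, and it has no halt. Row D can be reached through its limit-of-safety criterion, which is also a judgement, but its halt clause still refers only to Grades 3 and 4.

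**Step 2. Does a survivable event meet a stricter rule?** Yes. One Grade 4 event in one subject meets the 7.9 trigger unless it is accidental or due to NPC progression, and resumption follows DSMC review.

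**Step 3. Do 7.8 and row D agree on pulmonary events?**

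- Scope: the text of 7.8 and the table title exclude respiratory events, while row D includes drug-related pulmonary complications.
- Action: for infiltrates likely due to drug, the text of 7.8 allows withdrawal or dose decrease; row D requires withdrawal.

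Withdrawing the infant satisfies both. Decreasing the dose satisfies 7.8 and breaches row D. The conflict is therefore whether a dose decrease remains available for a drug-related pulmonary complication.

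**The case against.** The strongest reply is that this is a drafting slip with no practical effect. Any sensible team would treat death as at least Grade 4. The unacceptable-risk clause obliges the DSMC or Principal Investigator to terminate once that judgement is made, SAEs are submitted within 24 hours, and the DSMC can be convened at any time. Most of this stands: the omission is probably a slip, and the safeguards are real. Apart from SAE reporting, though, they depend on someone's judgement, which an automatic trigger is meant to replace.

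A related reply is that a fatal event passes through Grade 4 first. That is not assured on paper. Section 9.6 allows doses 3 to 12 as an outpatient, with discharge two hours after the infusion, so a death at home might have no recorded Grade 4 stage.

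Stronger readings are tempting but unsupported:

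- A reader might infer that dosing of other infants would continue after a death until the next scheduled DSMC review. Sections 7.9, 11.4 and 11.5 all permit earlier action, so the review schedule does not measure a delay.
- A reader might count the silence on Grade 5 in the withdrawal rules of 5.6 and 7.7 as further gaps. Those rules withdraw the affected subject, which is moot after death.
- A reader might infer that identical respiratory signs carry different required actions in 5.6, 7.7, 7.8 and 9.11. Section 5.6 adds a need for supplemental oxygen and 7.7 refers to a new oxygen requirement. Sections 5.6, 7.7 and 9.11 are permissive, and 9.11 names who decides on tolerability. Only row D mandates a single action.
- A reader might suspect that the respiratory counts in 11.4.2 displace 7.9. Nothing in the documents says so.

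**Conclusion.** Both parts hold in a limited form. Neither of the two grade-based halt clauses covers Grade 5, so the written rule is stricter for a survivable event than for a drug-related death. Table 1 row D contradicts the table's stated scope, and it contradicts the dose-decrease option in 7.8 for drug-related pulmonary complications.

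The points should be corrected because they concern infant safety and cost little. They change no endpoint, analysis or dose level, and they do not show that a death would go unreviewed.

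The conclusion assumes that the rules are read literally and that Table 1 carries no note altering row C or row D. The heading of its decision column has an asterisk with no footnote in the available text, and rows A and B end in incomplete phrases, so such a note cannot be ruled out. It would bear most on the pulmonary part.

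**What to change.** 1. In 7.9, change the single-subject trigger to 'any Grade 4 or 5 adverse event', keeping the existing exceptions. In Table 1 row D, write 'Grade 4 or 5' in both the criterion and the halt clause, so that a drug-related death is handled by row D and not row C.
2. Make row D and 7.8 agree on drug-related pulmonary complications. Either remove them from row D so that the 7.8 rule governs, or remove the dose-decrease option for them from 7.8 and drop the respiratory exclusion from Table 1. The choice is clinical and belongs to the sponsor-investigator and the DSMC.

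The cost is a short wording amendment to 7.8 (with Table 1) and 7.9. The downside is a possible dosing pause for DSMC review after a death. Phase 1 doses are 4 ± 1 days apart, so a gap of more than 4 + 1 = 5 days since the last dose takes an infant outside the window. At two doses a week, each week of pause affects about 2 of the 12 doses.

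One limit remains. Because the NPC-progression exception stays in 7.9, the change does not settle in advance a death whose attribution to the disease is disputed.
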